#### **6.6.5 Safety Data Collection**

The following safety information will be collected from the time the parental consent and patient assent forms are signed: AEs of Special Interest and SAEs. The Physician will assess and record the AE in detail including the date of onset, description, severity, time course, duration and outcome, relationship of the AE to treatment, an event diagnosis, if known, and any action(s) taken. For SAEs considered "possibly related," "probably not related" and "not related" to the registry treatment, the Physician will provide the alternative etiology of the event. Information about medications taken to treat the SAE or the Adverse Event of Special Interest will be collected.

During the first 5 years of the registry, all available patient data, including SAEs, AESI as defined by the protocol and pregnancies will be collected at each doctor's visit. However, SAEs, AESI and pregnancy information can be collected at any time during the registry, not only at each doctor's visit. During Years 6 through 10 of the registry, patient data will be collected annually, including SAEs, a subset of AESI that includes congestive heart failure, malignancies, AEs at least possibly related to and/or leading to discontinuation of registry treatment, and pregnancies (Figure 1). Polyarticular JIA patients 2 to < 4 years of age, in countries with available local approval for this group of patients at the time of consent to the registry, will have SAEs, AESI, and pregnancy (potentially at the age when patient can become pregnant) collected for the full 10 years as defined by the protocol (Figure 2). Patients who develop an SAE or Adverse Events of Special Interest (AESI) while in the registry will be followed throughout the patient's participation in the registry until satisfactory conclusion or until 70 days following the last registry dose (whichever is longer).

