### 7.1.3 Adverse Events of Special Interest

The Physician will monitor each patient for clinical and laboratory evidence for pre-defined Adverse Events of Special Interest at the Baseline visit and on a routine basis through Year 10 of the registry as mentioned in Section 6.5 Registry Duration.

AEs of Special Interest for this registry include:

Serious and nonserious opportunistic infections including the following bacterial, fungal, viral, and parasitic infections: Aspergillus, Blastomyces, Candida, Coccidioides, Cryptococcus, Cytomegalovirus, Histoplasma, Listeria, Nocardia, Paracoccidioides, Pneumocystis, Toxoplasma, Tuberculosis, Herpes, Bacillary angiomatosis, Mucormycosis, Progressive Vaccinia, Zygomycosis, BK virus, and JC virus.

Hypersensitivity reaction to Humira injection

Lymphoma

Hepatosplenic T-cell lymphoma

Non-melanoma skin cancer (NMSC)

Leukemia

Other malignancies (except lymphoma and NMSC)

Immune reactions including lupus, lupus-like reactions, and severe allergic reactions

CNS demyelinating disorders (including MS and Guillain-Barré syndrome and optic neuritis)

Hematologic events that are serious or lead to permanent discontinuation of treatment (e.g., aplastic anemia, granulocytopenia, granulocytes maturation Arrest, Leucopenia, Neutropenia, Pancytopenia, and Thrombocytopenia)

Hepatic events that are serious or lead to permanent discontinuation of treatment (e.g., persistent liver function test abnormalities, acute liver failure, and other serious hepatic events)

Vasculitis

Diverticulitis

Intestinal perforation

Congestive heart failure (CHF)

Severe CPK elevations (defined as CTC grade 3 and above) and associated clinical syndromes

New onset seizure disorders defined as any new epilepsy disorder diagnosed within the timeframe of the registry

Antiphospholipid syndrome and associated autoantibodies

New onset or worsening of Psoriasis

All events leading to premature discontinuation of treatment (Note: limited to only Adverse Events of Special Interest [listed above] leading to premature discontinuation for patients participating in the direct to HCP process)

All events that are probably or possibly related to treatment (Note: limited to only Adverse Events of Special Interest [listed above] that are probably or possibly related to treatment for patients participating in the direct to HCP process)

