### 7.1.6 Relationship to Pharmaceutical Product

The Investigator will use the following definitions to assess the relationship of the AE to the use of pharmaceutical product:

**Probably Related** An AE has a strong temporal relationship to pharmaceutical product or recurs on re-challenge and an Other cause of event is unlikely or significantly less likely.

**Possibly Related** An AE has a strong temporal relationship to the pharmaceutical product and an Other cause of event is equally or less likely compared to the potential relationship to pharmaceutical product.

**Probably Not Related** An AE has little or no temporal relationship to the pharmaceutical product and/or a more likely Other cause of event exists.

**Not Related** An AE is due to an underlying or concurrent illness or effect of another drug and is not related to the pharmaceutical product (e.g., has no temporal relationship to pharmaceutical product or has a much more likely other cause of event).

If an Investigator's opinion of possibly, probably not, or not related to pharmaceutical product is given, an Other cause of event must be provided by the Investigator for the SAE.

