### **10.3.1 Analysis of Observational SAEs and AEs of Special Interest**

The number and percent of patients experiencing SAEs and AEs of Special Interest during the registry, regardless of whether the AEs are reported during or after the Humira or MTX treatment, will be tabulated by body system and Medical Dictionary for Drug Regulatory Activities (MedDRA®) preferred term. Rates (event per 100 patient year of observation) of SAEs and AEs of Special Interest and the 95% confidence interval will be provided. The AEs summaries will also include SAEs and AEs of Special Interest collected through the HCP process. The last contact date is defined as the last date of registry or direct to HCP process participation, whichever occurs later.

The summaries will be provided using data from the first day in registry through the last contact irrespective of drug treatment duration.

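### Non-serious events off the named AESI list count only if judged related to treatment or followed by stopping it, so AESI rates can differ between arms through attribution or stopping alone

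*Supplement*

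**What the plan says.** **Collection.** Section 6.6.5 limits the safety data: "The following safety information will be collected from the time the parental consent and patient assent forms are signed: AEs of Special Interest and SAEs". Section 7.1.1 speaks of monitoring for all adverse events, but only as set out in 6.6.5.

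**The AESI list (7.1.3).** Many named items count whatever the cause, for example "Serious and nonserious opportunistic infections", malignancies, vasculitis and CHF. Some named items are conditional: "Hepatic events that are serious or lead to permanent discontinuation of treatment", with the same condition on hematologic events. One can occur only under Humira: "Hypersensitivity reaction to Humira injection". The list closes with two open items, "All events leading to premature discontinuation of treatment" and "All events that are probably or possibly related to treatment". For patients in the direct-to-HCP process, both open items are limited to events already on the list.

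**Years 6 to 10.** For patients aged 4 to 17, Section 6.0, Table 1 note f, 6.6.5 and 7.1.7 reduce the AESI to CHF, malignancies, and events at least possibly related or leading to discontinuation.

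**Relatedness (7.1.6).** The physician rates the relation to a single pharmaceutical product. The lowest category reads "An AE is due to an underlying or concurrent illness or effect of another drug and is not related to the pharmaceutical product".

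**Analysis.** Section 10.3.1 states "Rates (event per 100 patient year of observation) of SAEs and AEs of Special Interest and the 95% confidence interval will be provided". Sections 10.3.2 and 10.3.3 give the same rates per patient-year of exposure. Tables are by body system and preferred term. A summary by severity and relationship is planned in 10.3.2 and 10.3.3, but not in 10.3.1. Section 5.0 makes the MTX arm the reference group.

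**The concern.** The AESI rate adds two different quantities. Most named events are counted on occurrence. Off-list non-serious events are counted on occurrence and on a judgment or action by a physician who prescribed the drug and knows what it is. The registry is observational and the documents describe no causality adjudication. If physicians attribute events to one drug more readily than to the other, or stop one more readily, the AESI rates separate even when the children have the same events at the same frequency.

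Long-term safety is the primary objective. An AESI rate with a confidence interval, set beside a reference group, will be read as a safety contrast even though no test is planned. The analysis cannot repair this afterwards, because non-serious events that were neither attributed nor followed by a stop are not in the database.

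In Years 6 to 10 the dependence widens for ages 4 to 17. On the listed subset, a non-serious opportunistic infection or new psoriasis then counts only if it is judged related or leads to discontinuation.

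**Working it through.** **1. The plan's own figure.** The documents give no AESI rate or attribution share to recompute. The one safety calculation is in 10.6: about 97% power, 1500 patient-years, 4.8 against 2.8 serious infectious AEs per 100 patient-years, two-sided 0.05. Expected events are 1500 × 0.028 = 42 and 1500 × 0.048 = 72. The normal approximation gives (72 − 42 − 1.96√42)/√72 = (30 − 12.70)/8.49 = 2.04, a power of 97.9%. The exact Poisson test, rejecting at 56 or more events, gives 97.8%. The stated figure is reproduced to within a point. It concerns serious events in one arm, which are collected regardless of attribution, so this concern does not touch it.

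**2. How attribution enters the AESI rate.** Let B be the rate of named AESI and R the true rate of off-list non-serious events, both per 100 patient-years and equal in the two arms. Let q be the share of off-list events that are attributed or followed by a stop.

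- AESI rate in an arm = B + R × q
- Overall AESI rate ratio = (B + R × q₂)/(B + R × q₁)
- Open items alone: ratio = q₂/q₁, for example 0.20/0.10 = 2.0 or 0.15/0.10 = 1.5

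All values of B, R and q below are assumptions; none is in the documents.

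| q₁ vs q₂ | R = 20, B = 5 | R = 50, B = 5 | R = 100, B = 2 |
|---|---|---|---|
| 20% vs 20% | 9/9 = 1.00 | 15/15 = 1.00 | 22/22 = 1.00 |
| 20% vs 30% | 11/9 = 1.22 | 20/15 = 1.33 | 32/22 = 1.45 |
| 20% vs 40% | 13/9 = 1.44 | 25/15 = 1.67 | 42/22 = 1.91 |
| 10% vs 30% | 11/7 = 1.57 | 20/10 = 2.00 | 32/12 = 2.67 |

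Named events dilute the ratio: doubling q from 20% to 40% gives 1.44 to 1.91, not 2.0. The direction depends on which arm's drug is suspected more often.

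**3. Which drug counts for a Humira+MTX patient.** The passages point both ways.

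- *Either drug:* Section 6.0 describes Humira-arm therapy as Humira alone or together with MTX. Section 6.6.11 calls both drugs registry treatments. Section 7.1.7 ties AESI reporting after the last dose to a relation with either drug.
- *Humira only:* Section 7.1.6 rates one undefined product and lets an event be assigned to another drug. Section 10.2 computes Humira-arm exposure from Humira doses only.

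An MTX side effect in a combination patient is related under the first reading and may be rated not related under the second. So between none and all of such events could be lost from the relatedness item in the Humira arm, depending on how sites read the text.

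**The case against.** The strongest reply has five parts.

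- **The tables already help.** Preferred-term tables let tuberculosis or lymphoma be read apart from nausea, and 10.3.2 and 10.3.3 add a relationship summary. This stands in part. The relationship summary mixes related named events with open-item events and is absent from 10.3.1. No planned table separates the two kinds of event.
- **Little depends on it.** MTX is a reference group, no between-arm AESI test is planned, and SAEs and the sizing do not depend on attribution. This stands and limits the importance of the point.
- **Table layout and causality fields belong in the SAP and eCRF, which are not shown.** This stands for the layout, so the absence of a split is not an omission in itself. The AESI definition, the collection rule and the product to which relatedness refers are protocol matters.
- **A table of named AESI is not free of the problem.** It would still hold a Humira-only item and hepatic and hematologic items that depend on stopping. This is correct, and the fix takes it into account.
- **The arm asymmetry is not a rule.** A reader might infer that MTX nausea in a Humira+MTX child is excluded while the same event in the MTX arm counts. The documents do not say so. Sections 6.0, 6.6.11 and 7.1.7 support counting events related to either drug. What remains is an ambiguity.

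**Conclusion.** The point holds as a risk built into the definition and the reporting. AESI rates can differ between the Humira and MTX arms through attribution or stopping behaviour alone, and the planned tables do not isolate the part that is exposed to this. That rests on the text of 6.6.5, 7.1.3 and 10.3.1 to 10.3.3 and needs no outside figure.

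The size is unknown. Ratios of about 1.2 to 2.7 follow from assumed attribution shares and event rates and show only what is possible. A reader might infer that the rates do differ, that they differ by a factor of two, or that most non-serious events are affected. The documents support none of these: they contain no attribution shares, event counts or combination-therapy share, and a ratio of 2.0 from a doubled share applies to the open items only.

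The reference drug for Humira+MTX patients is unsettled and should be defined.

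**What to change.** 1. **Split the AESI tables in 10.3.1 to 10.3.3.** Report named AESI separately from the two open items, and label the open-item tables as dependent on attribution or discontinuation.
2. **State the basis of the descriptive Humira-MTX contrast.** Use all SAEs, plus named AESI that need neither a causality rating nor a stop. Leave out the Humira-injection hypersensitivity item and restrict hepatic and hematologic items to serious events. For ages 4 to 17, use events and person-time from Years 1 to 5, except for CHF and malignancies, which are collected to Year 10.
3. **Define relatedness in 7.1.6.** State that for combination patients a relation to either Humira or MTX counts as related to registry treatment, and use one term for this throughout.

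**Cost.** The split uses data already collected and is a programming step. The definition is one sentence plus site guidance. Two AESI figures replace one. The split cannot recover unattributed non-serious events that were never collected, so the open-item rates remain a description of what physicians attributed or stopped for.

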#### **7.1.4 Serious Adverse Events**

If an AE meets any of the following criteria, it is to be reported to AbbVie as an SAE within 24 hours of the site being made aware of the SAE. SAEs are required to be reported to AbbVie through Year 10.

Death of Patient	An event that results in the death of a patient.
Life-Threatening	An event that, in the opinion of the Investigator, would have resulted in immediate fatality if medical intervention had not been taken. This does not include an event that would have been fatal if it had occurred in a more severe form.
Hospitalization or Prolongation of Hospitalization	An event that results in an admission to the hospital for any length of time or prolongs the patient's hospital stay. This does not include an emergency room visit or admission to an outpatient facility.
Congenital Anomaly	An anomaly detected at or after birth, or any anomaly that results in fetal loss.

Persistent or Significant Disability/Incapacity	An event that results in a condition that substantially interferes with the activities of daily living of a registry patient. Disability is not intended to include experiences of relatively minor medical significance such as headache, nausea, vomiting, diarrhea, influenza, and accidental trauma (e.g., sprained ankle).
Important Medical Event Requiring Medical or Surgical Intervention to Prevent Serious Outcome	An important medical event that may not be immediately life-threatening or result in death or hospitalization, but based on medical judgment may jeopardize the patient and may require medical or surgical intervention to prevent any of the outcomes listed above (i.e., death of patient, life-threatening, hospitalization, prolongation of hospitalization, congenital anomaly, or persistent or significant disability/incapacity). Examples of such events include allergic bronchospasm requiring intensive treatment in an emergency room or at home, blood dyscrasias or convulsions that do not result in inpatient hospitalization, or the development of drug dependency or drug abuse.
Spontaneous Abortion	Miscarriage experienced by registry patient.
Elective Abortion	Elective abortion performed on registry patient.

An elective surgery/procedure scheduled to occur during the registry will not be considered an adverse event if the surgery/procedure is being performed for a pre-existing condition and the surgery/procedure has been pre-planned prior to registry entry. However, if the pre-existing condition deteriorates unexpectedly during the registry (e.g., surgery performed earlier than planned), then the deterioration of the condition for which the elective surgery/procedure is being done will be considered an adverse event.

### **7.1.5 Adverse Event Severity**

The Investigator will use the following definitions to rate the severity of each AE:

Mild	The AE is transient and easily tolerated by the patient.
Moderate	The AE causes the patient discomfort and interrupts the patient's usual activities.

**Severe** The AE causes considerable interference with the patient's usual activities and may be incapacitating or life-threatening.

### 7.1.6 Relationship to Pharmaceutical Product

The Investigator will use the following definitions to assess the relationship of the AE to the use of pharmaceutical product:

**Probably Related** An AE has a strong temporal relationship to pharmaceutical product or recurs on re-challenge and an Other cause of event is unlikely or significantly less likely.

**Possibly Related** An AE has a strong temporal relationship to the pharmaceutical product and an Other cause of event is equally or less likely compared to the potential relationship to pharmaceutical product.

**Probably Not Related** An AE has little or no temporal relationship to the pharmaceutical product and/or a more likely Other cause of event exists.

**Not Related** An AE is due to an underlying or concurrent illness or effect of another drug and is not related to the pharmaceutical product (e.g., has no temporal relationship to pharmaceutical product or has a much more likely other cause of event).

If an Investigator's opinion of possibly, probably not, or not related to pharmaceutical product is given, an Other cause of event must be provided by the Investigator for the SAE.

### 7.1.7 Adverse Event Collection Period

Adverse Events of Special Interest will be reported any time after the last dose MTX or Humira if the Physician believes the event is related to MTX or Humira treatment. In the event Humira therapy is interrupted, SAEs and Adverse Events of Special Interest will be collected throughout the interruption. If treatment with MTX or Humira is permanently discontinued for any reason, the reason will be recorded, and the patient will be

encouraged to remain in the registry. For patients enrolled from the prior polyarticular juvenile idiopathic arthritis (JIA) Humira study, ongoing AEs will be collected within the primary clinical trial and will be captured as part of the patient's medical history in the registry.

During the first 5 years of the registry, all available patient data, including SAEs, AESI as defined by the protocol and pregnancies will be collected at each doctor's visit. However, SAEs, AESI and pregnancies can be collected at any time, not only at each doctor's visit. During Years 6 through 10 of the registry, patient data to be collected annually, including SAEs, a subset of AESI that includes congestive heart failure, malignancies, AEs at least possibly related to and/or leading to discontinuation of registry treatment, and pregnancies (Figure 1). Polyarticular JIA patients 2 to < 4 years of age in countries with available local approval for this group of patients at the time of consent to the registry will have SAEs, AESI, and pregnancy (potentially at the age when patient can become pregnant) collected for the full 10 years as defined by the protocol (Figure 2). Patients who develop an SAE or Adverse Event of Special Interest (AESI) while in the registry will be followed throughout the patient's participation in the registry until satisfactory conclusion or until 70 days following the last registry dose (whichever is longer).

For patients participating in the HCP process, safety data will be collected by the participating HCP using the HCP questionnaire on an annual basis. The questionnaire to be used through Year 5 focuses on the collection of Adverse Events of Special Interest (AESI), hospitalizations, surgeries, and death. The questionnaire to be used for Years 6 through 10 focuses on collection of a subset of AESI that includes congestive heart failure and malignancies, hospitalizations, surgeries, and death (Figure 1). In addition, for polyarticular JIA patients 2 to < 4 years of age in countries with available local approval for this group, Safety data will be collected by the participating HCP using the HCP questionnaire on an annual basis. The questionnaire will focus on collection of AESI, hospitalizations, surgeries, and death and will be collected for the full 10 years as defined by the protocol (Figure 2). The questionnaire may be completed by the registry physician

or the patient's current HCP (if the patient is no longer under the care of a registry physician).

The Follow-up received on any ongoing SAEs and/or AESI post registry conclusion should be reported using standard Post Marketing Spontaneous Reporting.

Follow-up contact can include a certified letter or phone call to the patient. All contact must be clearly documented in the patient's registry file.

[figure not shown]
All medications used to treat these events will also be captured. A complete list of the Adverse Events of Special Interest can be found in Section 7.1.3.

#### **7.1.8 Serious Adverse Event Reporting**

[figure not shown]
In the event of a SAE, and additionally, any nonserious event of malignancy in patients 30 years of age and younger, whether related to registry drug or not, the physician will notify the AbbVie Clinical Pharmacovigilance Team within 24 hours of the physician becoming aware of the event by entering the Serious Adverse Event or nonserious event of malignancy in patients 30 years of age and younger into the electronic data capture (EDC) system. Serious Adverse Events and nonserious events of malignancy in patients 30 years of age and younger, that occur prior to the site having access to the EDC system or if the EDC is not operable should be documented on the SAE Non-CRF paper forms and emailed to AbbVie Clinical Pharmacovigilance or faxed to AbbVie Clinical Pharmacovigilance within 24 hours of being made aware of the Serious Adverse Event.

For SAE concerns, contact the Immunology Safety Team at:

For any subject safety concerns, please contact the Primary Study Designated Physician listed below:

Should in case of subject safety concerns or medical emergencies the Primary Study Designated Physician be unavailable, please call the following central back-up number:

